**Donors enrolled in the prospective follow-up study will have additional specimens collected at 3 time points.**

At each visit, 48mL of whole blood will be collected:

- 1 x 9mL EDTA specimen tubes
- 3 X 9mL ACD specimen tube for PBMC preparation
- 1 x 6mL EDTA/ACD specimen tube
- 1 x 6mL serum tube

#### 4.5.1 Specimen collection procedures

All specimens will be collected using standardized aseptic technique, accessing the median cubital vein through the antecubital fossa. Venous blood will be collected after applying a superior tourniquet. Sufficient blood will be collected for the requirements detailed above. Specimens will be labeled, stored and transported as per the standard SANBS operating procedures. Additional study-specific specimen labels will be prepared and supplied by the Data Coordinating Centre (DCC). All disposables will be discarded in biohazardous containers as per local regulations and standard operating procedures.

#### **4.6 Survey Considerations and OMB Requirements**

An extensive risk factor interview will be completed by both cases and controls who participate in this study (**Appendix 7**). Objective 3 participants will also complete a brief clinical questionnaire at each visit (**Appendices 8 and 9**). All interview instruments will have to be approved for use by OMB. We are planning to allow for up to nine months to obtain clearance to use the instruments.

#### **4.7 Data Management**

The specifics of at least four data management systems will need to be developed by the REDS-III DCC, Research Triangle Institute:

1. Tracking system. SANBS is currently developing an operational tracking system for notification and counseling of donors with positive viral test results which will serve to identify potential participants. The specifications for that tracking system are included as **Appendix 6**. This document can serve as guide to the components that are necessary for a tracking system. In addition, a web-based Study Management System (SMS) will be designed to monitor enrollment of cases and controls, completion of questionnaires, blood sampling tasks and other required visit procedures for each enrolled participant in Objectives 1 and 2 and at follow-up visits for those enrolled in Objective 3. More specifically, this will require the development of a regular reporting system with which to closely monitor the demographic characteristics of cases to ensure the enrollment of properly matched controls at the specified ratio (1:3).
2. Laboratory database. Test result data for the additional laboratory testing mandated by this protocol and not part of usual SANBS procedure, will be entered into the SANBS main frame and uploaded via the supplementary file to the REDS-III South Africa HIV/HBV Biological Specimen Inventory (BSI) database.
3. Questionnaire database. ACASI interviews will be consolidated from laptops to a central database on a daily basis at SANBS using QDS Software, and then transferred weekly to RTI via a secure FTP server for QC and analysis.

4. Clinical questionnaires. Teleform forms completed at each visit during Objective 3 of the study will be scanned into a database at SANBS headquarters (Constantia Kloof), and transferred to RTI using standard procedures already in use for the REDS-III South Africa project.

## **4.8 Statistical Considerations**

To estimate the required sample size for the incident HIV and incident HBV groups and the control negative donors we focused on two different behaviors that have been separately associated with HIV and HBV infection in South Africa. For HIV infection we considered the risk factor of multiple sexual partners. For HBV we assumed scarification or other forms of body modification would be a potential route for HBV acquisition. Power analyses below indicate that with expected enrollment we will have sufficient power to detect odds ratios between 1.6 and 2.0 for putative incident HIV and HBV risk factors.

### **4.8.1 Sample size and power**

Sample size and power calculations for this study cannot be based on the assumption of independent donor sample selection. We will be selecting blood donation clinics that are similar to those clinics where the study cases were donated, and, then, from the selected clinics selecting controls. Consequently, the sampling and analytic approaches account for clustering at the clinic level. Computer simulations (Monte Carlo simulation) of the study population were run to determine the odds ratios we can detect based the assumptions of the exposure prevalence in the donor populations and the expected number HIV and HBV cases that we will be able to enroll in the study during a 3-year period. There were several factors examined in the Monte Carlo simulation, i.e., the expected number of cases, the expected number of controls per case, the correlation between proportion exposed for the cases and controls, the proportion exposed in the control group, and the difference in proportions between the controls and cases. Thus cross-classification of all of these factors created multiple experimental groups and 1,000 Monte Carlo simulations were run for each group. Calculations are based on alpha equal to 0.05, power equal to 0.8, and a two-sided test.

### **HIV Power Calculations**

For HIV we focused on multiple sexual partners (more than one partner at the same time, or at least two partners in the previous year) as a primary risk factor in South Africa, and estimated that the prevalence of multiple sexual partners in the control and case populations. We assumed a 10% difference in the prevalence of multiple sexual partners between cases and controls. Depending on the prevalence of multiple sexual partners in the control population the odds ratio that we will be able to detect with 80% or higher power is between 1.65 and 1.94 for

a study with 300 cases and 900 controls (Table 8). In the Monte Carlo, simulation estimates for odds ratios were similar regardless of the ratio of cases to controls, 1:1, 1:2, or 1:3. That is, a 1:1 ratio would allow for similar odds ratios to be detected. This analysis assumes that the selection of controls from the same geographic regions as cases will be consistent with the assumptions of inter cluster correlations that were defined for the Monte Carlo simulation power analysis. However, there is substantial uncertainty around how similar the behavioural exposures of cases and controls between different clusters (clinics) will be. For this reason we believe including a larger number of controls per case may be required in order for the team to ensure the study meets its primary objectives. Recall that we will be accepting virtually all cases so the only way to enlarge the sample is to include more controls. Also, including more controls will allow for secondary analyses of behavioural prevalence in donors without infection. For example, the study is interested in understanding the range of relatively common to less common risk factors for newly acquired infections in blood donors in South Africa. We want to be able to detect and report findings across a range of behavioural exposures. It is not expected the distribution of all behaviors will conform to the assumptions made for the Monte Carlo power analysis. Risks other than multiple sexual partners will have different prevalence in the donor population and may have smaller differences in exposure prevalence between cases and controls within each clinic. For these reason we are planning to enroll cases and controls in a ratio of 1:3.

Each year approximately 50 HIV NAT-only (anti-HIV negative) infections are identified in SANBS donors. Using LAg Avidity testing strategies an additional ~160 HIV-positive donations per year can be classified as recently acquired infections. With a likely participation proportion in the study estimated to be around 50%, it will take 3 years to accrue the target number of 300 recently acquired HIV cases in this study. Our enrollment projections suggest that over a 3-year period we will be able to enroll up to 300 recently acquired HIV infections. We will not be able to enroll more cases and so to slightly enhance power we will increase the number of controls in a ratio of 1:3 as described above because controls will be easier to obtain within the available time frame and infrastructure available to conduct the study.

Table 8. Sample size and achieved odds ratios assuming 80% power for incident HIV infections.

Behavioural Exposure Proportion		Detectable Odds Ratio	Case:Control = 1:3		
Control	Case		Case	Control	Total
0.15	0.25	1.94	300	900	1,200
0.20	0.30	1.74	300	900	1,200
0.25	0.35	1.65	300	900	1,200

### HBV Power Calculations

For HBV infections we considered scarification prevalence in rural South Africa and similar body modification such as tattoo and body piercing and more recent study from Nigeria. These two papers reflect divergent proportions of scarification in HBV negative individuals as high as 90% in the older paper from South Africa to as low as 3% in the more recent paper from Nigeria. Because we anticipate that the prevalence of body scarification in the population we wish to include in this study will be somewhere between these values, we chose an approximate midpoint for the purpose of sample size estimation as the prevalence of scarification and other body modification in the HBV negative population.

A similar computer simulation approach as that used for HIV was used to estimate the detectable odds ratios for behavioural exposures associated with incident HBV (Table 9). Our enrollment projections suggest that over a 3-year period we will be able to enroll approximately 150 recently acquired HBV infections. With the ratio of cases to controls of 1:3 we will have sufficient power to be able to estimate the odds of HBV in people with scarification and similar body modification between 1.87 and 1.96 depending prevalence scarification and similar body modification in the control population.

Previously SANBS has reported approximately 40-45 true HBV window period ID-NAT yields per year. In addition, in preliminary anti-HBc testing conducted in early 2012, during 6 months 29 donors were HBsAg-positive, anti-HBc-negative, giving an estimate annual number of expected HBsAg-positive, anti-HBc-negative participants of ~60. These numbers together suggest that at best we might have ~100 recently acquired HBV infections per year that we could include in the study. With a likely participation proportion in any risk factors assessment estimated to be around 50%, it should take 3 years to accrue the target number of 150 recently acquired HBV cases in this study. The controls identified for the HIV case comparison will be used for the HBV comparison. Separate controls to compare to incident HBV will not be selected.

Table 9. Sample size and achieved odds ratios assuming 80% power for incident HIV infections.

Behavioural Exposure Proportion		Detectable Odds Ratio	Case:Control = 1:3		
Control	Case		Case	Control	Total
0.45	0.60	1.87	150	450	600
0.50	0.65	1.90	150	450	600
0.55	0.70	1.96	150	450	600

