Similarly for HBV, the window period for HBV ID-NAT from the time of potential infectivity that could lead to infection transmission to the ability of current technology to detect is approximately 15 days and HBV ID-NAT positivity precedes Hepatitis B surface antigen (HBsAg) positivity by approximately 17 days (pre HBsAg window period 32 days from potential infectivity) on average. If a donation tests HBV-NAT positive, HBsAg positive, and anti-HBc negative, the infection is also recently acquired (approximately between 32 and 95 days). SANBS identified 476 HBV ID-NAT yields in 5 years however over 50% were also anti-HBc positive, indicating prevalent versus recently acquired infection. Thus, there were approximately 216 true HBV ID-NAT yields in the five year period, resulting in 40-45 individuals per year that were confirmed “window period” donors. In addition SANBS detected 3414 concordant HBV-NAT positive and HBsAg positive donations of which approximately 5% (170) were anti-HBc negative in five years, giving an additional 30-35 incident infections per annum.

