To minimize any community rumors or individual anxieties linking the research to HIV status, recruitment scripts and study informational materials will emphasize that both HIV-positive, HBV-positive, and HIV and HBV-negative participants are being enrolled in order to identify and compare prevailing risk factors among the positive and negative groups. All donors will complete the same ACASI questionnaire.

**Objective 3 Participants:** Selected donors with incident HIV infections who were identified and enrolled during the first two years of Objective 1a and 2a recruitment will be prospectively enrolled into Objective 3 of the study. Participants in Objective 3 will be a subset of Objective 1a and 2a participants who meet eligibility criteria and are willing to participate in this objective. Elite controllers will include those identified in the first 2.5 recruitment years of the study. Donors will be consented and enrolled either during the post-test HIV counseling visit or shortly thereafter timed with Objective 1 enrollment and specimens collected on the day of enrollment and at 3 follow-up visits for CD4, viral load and cytokine profiling as well as PBMC preparations (**Consent in Appendix 4**). The total volume of blood collected at each follow-up visit will not exceed 48 mL.

**Study Locations:** The study will be located in geographic areas within the SANBS catchment where the proportion of donors with HIV and HBV infectious markers is high and where there is documented evidence of good success in notifying donors. We will conduct the study in 5 locations in 4 Provinces; Gauteng (Johannesburg and Pretoria), KwaZulu Natal (Durban), Mpumalanga Province and the Eastern Cape Province. For operational purposes, SANBS divides the Gauteng Province into 3 operational zones, namely “Egoli”, “Vaal” and “Northern”, with Johannesburg the main metropolitan area in Egoli and Pretoria the main metropolitan area in the Northern zone.

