## **HBV**

To date, notifying donors with HBV NAT-yield infections has not been as successful as HIV notifications. In addition, tracking of this information is not currently routine in SANBS. Based on information obtained from the Reference Laboratory in Constantia Kloof with data covering a three month period January – March 2012, successful return and notification for donors with HBV-yield donations is significantly higher in Durban area compared to Johannesburg (Table 7). This is also an area with an appreciably higher burden of HBV infection. As with HIV, we believe we will be able to enroll nearly all persons who return for notification for recently acquired HBV infection into the study given that they will be on site for notification.

Table 7. HBV notification and counseling success rates, January – March 2012.

	JHB (Zone 1)	DBN (Zone 2)	Total
HBV	28	15	43
HBV returns	6	6	12
Return rate HBV	21%	40%	28%
*Untyped	6	5	11
Untyped returns	4	4	8
Total returns	10	10	20
Combined return rate	29%	50%	37%
*Most untyped yields that confirm are HBV therefore are included.			

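### The accrual projections of 300 HIV and 150 HBV cases apply 50% participation to SANBS-wide counts although only five of seven zones take part; the shortfall matters mainly for HBV

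*Protocol*

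**What the plan says.** Under HBV Power Calculations (Protocol 4.8.1) the annual HBV base has two parts. The first is NAT yields: "Previously SANBS has reported approximately 40-45 true HBV window period ID-NAT yields per year". The second is concordant infections without core antibody: "during 6 months 29 donors were HBsAg-positive, anti-HBc-negative", taken as about 60 a year. The sum is put at about 100 a year, which the protocol itself calls a best case. Participation is then "estimated to be around 50%, it should take 3 years to accrue the target number of 150 recently acquired HBV cases". Under HIV Power Calculations, about 50 NAT-only and about 160 LAg-recent infections a year, at about 50% participation, lead to the statement that "it will take 3 years to accrue the target number of 300 recently acquired HIV cases in this study".

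Study Locations (4.2.2 Participant Enrollment) says: "We will conduct the study in 5 locations in 4 Provinces; Gauteng (Johannesburg and Pretoria), KwaZulu Natal (Durban"), plus Mpumalanga and the Eastern Cape. Section 4.1 likewise speaks of up to five of the seven zones. Vaal and Free State/Northern Cape are not on the list. The paragraph on cases in 4.2.2 expects at most half of recently infected donors to return. On HBV the protocol adds: "To date, notifying donors with HBV NAT-yield infections has not been as successful as HIV notifications". Table 7 there reports a return of 28%, or 37% with untyped yields.

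**The concern.** The annual counts cover all SANBS donors, but cases can be enrolled only in the study zones. The projection therefore multiplies the wrong base by a participation rate that the protocol elsewhere treats as an upper limit. For HBV, the protocol's only return data lie below that rate.

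Table 9 is calculated at 150 HBV cases and Table 8 at 300 HIV cases. If fewer cases are to be expected, the stated 80% power for HBV odds ratios of 1.87 to 1.96 (Objective 1b) rests on a number the design is not set up to deliver. The HIV section says that more cases cannot be enrolled, so a shortfall could not simply be made up by recruiting harder.

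**Working it through.** **Reproducing the plan.** Accrual = annual infections x 3 years x participation.
- HBV: 100 x 3 x 0.50 = 150, as stated.
- HIV: (50 + 160) x 3 x 0.50 = 315, stated as up to 300.

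Both follow only if all zones contribute.

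**Share held by the five study zones** (Table 3; Eastern Cape, Egoli, KwaZulu Natal, Mpumalanga, Northern).
- HIV: (24 + 43 + 83 + 35 + 52)/300 = 237/300 = 79.0%.
- HBV: (18 + 34 + 60 + 30 + 31)/248 = 173/248 = 69.8%.

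**Zone limit alone, at 50%.**
- HIV: 630 x 0.790 = 498 eligible; x 0.50 = 249.
- HBV: 300 x 0.698 = 209 eligible; x 0.50 = 105.
- Participation needed for the targets: 300/498 = 60% for HIV and 150/209 = 72% for HBV, both above the 50% maximum.

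**With observed return rates.**
- HBV, Table 7: 12/43 = 28% gives 209 x 0.28 = 59. With untyped yields, (12 + 8)/(43 + 11) = 20/54 = 37% gives 209 x 0.37 = 77.
- HIV, Table 6, counselled by SANBS in the five zones: (124 + 32 + 25 + 44 + 52)/(172 + 139 + 80 + 118 + 120) = 277/629 = 44.0%, giving 498 x 0.440 = 219. Adding those counselled elsewhere, (277 + 70)/629 = 55.2%, gives 275, still below 300.

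**Power for Table 9** (0.45 v 0.60, 0.50 v 0.65, 0.55 v 0.70; two-sided 0.05; normal approximation for two independent proportions, no clustering). Each entry is the range over the three rows.

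| HBV cases | Power, 1:3 | Power, 900 controls | Detectable OR at 80%, 1:3 (control 0.50) |
|---|---|---|---|
| 150 | 0.89-0.91 | 0.93-0.94 | 1.71 |
| 105 | 0.76-0.78 | 0.83-0.85 | 1.90 |
| 77 | 0.63-0.65 | 0.72-0.74 | 2.13 |
| 59 | 0.52-0.53 | 0.61-0.62 | 2.40 |

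Section 4.8.1 says that independence cannot be assumed. Clustering lowers every power in this table, and the documents give no correlation from which to compute by how much.

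**Power for Table 8** (10-point differences, 1:3, no clustering): 0.91-0.97 at 300 cases, 0.85-0.93 at 249, 0.81-0.90 at 219.

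**Objective 3.** The plan is 50 a year x 2 years x 0.50 = 50. With the zone share this is 50 x 0.79 = about 40.

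**The case against.** The best defence has four parts.

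- **The Table 7 sample.** It covers 43 donors (54 with untyped) over three months, NAT yields only. The 95% Wilson interval for 20/54 is 25-50%, so 50% is not clearly excluded. About 60 of the 100 yearly HBV cases are HBsAg-positive without core antibody, and no return rate exists for them. The protocol changes HBV notification and adds research staff, and it expects HIV notification to improve. This stands as a reason not to treat 59-77 as a forecast. No improved rate is given, however, and the projection still uses 50%. The zone limit alone removes 30% of HBV cases.
- **The controls.** HBV controls come from the HIV control pool, so up to 900 may be available rather than three per case. This also stands: at 105 cases, power is then 0.83-0.85 before clustering. At 77 and 59 cases it remains below 80%.
- **HIV.** Table 6 pools incident and prevalent infections, while NAT-yield donors get priority, so 44% may understate return. Even at 219 cases, power stays above 0.80 before clustering.
- **Objective 3.** It is mainly descriptive and makes no power claim. The projection is still too high, but little depends on it.

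Three stronger readings are tempting and not supported.

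- A reader might infer that the Table 9 odds ratios are out of reach at any realistic case number. At 105 cases the detectable odds ratios at 1:3, without clustering, are 1.89, 1.90 and 1.94, close to Table 9's 1.87, 1.90 and 1.96. What is lost there is the allowance for clustering.
- A reader might infer that site choice contradicts its stated reason, "where there is documented evidence of good success in notifying donors". Table 6 does show lower success in the chosen zones (44%) than in the omitted ones (90/124 = 73%), but Vaal contributes only April to June because it had no MLO before. There is also a second criterion, a high proportion of infected donors, and the three zones with the highest HIV proportions are all chosen.
- A reader might lower the HBV base to 70-80 a year, because the Background counts concordant cases as "giving an additional 30-35 incident infections per annum". That figure rests on a rough 5% share; the later direct count supports about 60.

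**Conclusion.** The accrual figures are wrong as written, chiefly for HBV. On the protocol's own participation rate, the five zones should yield about 249 HIV and 105 HBV cases, which is 17% and 30% below the 300 and 150 used in Tables 8 and 9. If HBV return stayed where Table 7 found it, the number would be about 59-77, and neither 1:3 sampling nor all 900 controls would give 80% power for the Table 9 differences. At 105 cases the answer depends on how many controls are used and on the clustering. For HIV the shortfall is real, but its effect on power is small.

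This rests on one main assumption: that the Table 3 zone split, which is for NAT-only infections in 2006-2010, also applies to LAg-recent HIV and to HBsAg-positive, core-antibody-negative HBV cases.

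**What to change.** 1. In 4.8.1, restate expected accrual for the five study zones, giving the zone share used. Show HBV at 50% and at the two Table 7 rates (about 105, 77 and 59).
2. Re-run the clustered simulation at those HBV numbers and re-issue Table 9, stating how many controls enter the HBV comparison: three per case, or the full pool.
3. Add a row to Table 8 at about 220-250 HIV cases.
4. Scale the Objective 3 projection to about 40 NAT yields in two years at 50%.
5. If a participation rate above 50% is expected after the notification changes, state it with its basis.
6. Optionally, note beside the site-selection sentence that Table 6 notification success is lower in the chosen zones than in the omitted ones.

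The cost is a simulation re-run and text edits. No extra participants are needed; the stated figures become less favourable.

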#### 4.9 Analytic Approach

Data analysis will be conducted in four phases: exploratory, adjustment for missing data, descriptive, and modeling. The first two phases, exploratory data analysis and adjustment for

missing data, will be conducted independently of the analyses for the specific objectives. The second two phases, descriptive data analysis and modeling, will be specifically tailored for each objective.

The exploratory data analysis phase will investigate the information provided in the data sets to determine: type of variable, valid values, level of missingness, and, if applicable, coding schemes. In addition, if there is any information available about relationships among variables, these relationships will be checked for logical consistency. Any data anomalies or logical inconsistencies identified during this phase of the analysis will be resolved. This will provide a relatively clean data set for the following phases of the data analysis.

The adjustment for missing data phase will minimize the potential bias from missing data. Virtually all data collection efforts experience the challenge of missing data. Typically, the missing data are not missing completely at random. Consequently, failure to account for the missing data, e.g., available or complete case analysis, can *potentially* lead to bias in the estimates produced. To investigate the potential for bias from the nonresponse, we will conduct a nonresponse bias analysis. Given the results of this analysis, which usually indicates that there is the potential for bias, we will use weight adjustments and/or multiple imputation to account for the missing values, and, therefore, minimize the potential bias.

The purpose of objective 1a is to identify the demographic and behavioural risk factors associated with incident HIV infection among blood donors in South Africa previously identified as “NAT-yield” and other recently acquired infection based on LAg Avidity testing as compared to controls. The outcome variable is whether or not a blood donor has HIV infection. That is, a binomial variable. The predictor variables believed to be associated with HIV in blood donors will include recent change in sexual partner, older male/younger female sexual partnership, a greater number of recent sexual partners, unprotected receptive anal intercourse, and lower socioeconomic status. Other possible predictor variables, e.g., behavioural variables, will be examined to understand their relationship to whether or not the blood donor has HIV infection. The association between the outcome variable and a predictor variable will be examined using categorical data analysis techniques. Bivariate analysis will be conducted using Chi-square tests. Analyses that include more than one predictor variable will be conducted using multiple logistic regression, which may include interaction terms. In addition, nonparametric modeling will be used when there are multiple predictor variables.

The purpose of objective 1b is to identify the demographic and behavioural risk factors associated with incident HBV infection among blood donors in South Africa previously identified as “NAT-yields” and which are anti-HBc negative. The outcome variable is whether or not blood donor has HBV infection. That is, a binomial variable. The predictor variables believed to be associated with HIV in blood donors will include greater number of recent sexual partners, recent scarification/tattoo/body markings, and history of personal contact with an HBV-infected

person. Other possible predictor variables, e.g., demographic variables, will be examined to understand their relationship to whether or not the blood donor has HBV infection. The association between the outcome variable and predictor variable will be examined using categorical data analysis techniques. Bivariate analysis will be conducted using Chi-square tests. Analyses that include more than one predictor variable will be conducted using multiple logistic regression, which may include interaction terms. In addition, nonparametric modeling will be used when there are multiple predictor variables.

The purpose of objective 2a is to determine HIV subtype and drug resistance profiles among HIV positive donors with recently acquired infection based on year of donation and site of collection, and correlate findings with donor demographics and risk behaviors derived in objective 1a. The outcome variable is HIV subtype. That is, a nominal categorical variable. The predictor variables believed to be associated with HIV subtype are year of donation and site of collection. Other variables, e.g., demographic variables and predictor variables identified in objective 1a, will be examined to understand their relationship to HIV subtype. The association between the outcome variable and predictor variable will be examined using categorical data analysis techniques. Bivariate analysis will be conducted using Chi-square tests. Analyses that include more than one predictor variable will be conducted using generalized logit models, which may include interaction terms. In addition, nonparametric modeling will be used when there are multiple predictor variables.

Objective 2a will also include analyzing drug resistance. The outcome variable is whether or not a blood donor is drug resistant to HIV treatment. That is, a binomial variable. The predictor variables will be HIV subtype, demographic variables, predictor variables identified in objective 1a, and predictor variables identified in the HIV subtype analysis in objective 2a. These predictor variables will be examined to understand their relationship to drug resistance. The association between the outcome variable and predictor variable will be examined using categorical data analysis techniques. Bivariate analysis will be conducted using Chi-square tests. Analyses that include more than one predictor variable will be conducted using multiple logistic regression which may include interaction terms. In addition, nonparametric modeling will be used when there are multiple predictor variables.

Finally, objective 2a will examine the relationship between the proportion of donors identified with incident HIV infection containing drug resistance mutations and the proportion of HIV-positive individuals receiving anti-retroviral therapy at a population-level in South Africa using available published data on the overall South Africa population. Given that we are able to identify sufficiently detailed population data, first, we will visually examine the relationship between the two types of proportions. Based on the visual examination and a sufficient amount of data, we will regress the proportion of donors identified with incident HIV infection containing drug resistance mutations on the proportion of HIV-positive individuals receiving anti-retroviral therapy at a population-level. Model diagnostics will determine whether or not

an appropriate model of the relationship has been determined. In addition, nonparametric modeling will be used to determine if a relationship exists.

The purpose of objective 2b is to determine HBV genotype profiles among HBV positive donors with recently acquired infection based on year of donation and site of collection, and correlate findings with donor demographics and risk behaviors derived in objective 2a. The outcome variable is HBV genotype. That is, a nominal categorical variable. The predictor variables believed to be associated with HBV genotype are year of donation and site of collection. Other variables, e.g., demographic variables and predictor variables identified in objective 2a, will be examined to understand their relationship to HBV genotype. The association between the outcome variable and predictor variable will be examined using categorical data analysis techniques. Bivariate analysis will be conducted using Chi-square tests. Analyses that include more than one predictor variable will be conducted using generalized logit models, which may include interaction terms. In addition, nonparametric modeling will be used when there are multiple predictor variables.

The purpose of objective 3 is to prospectively characterize the virology, immunology and natural history of incident HIV infection among a cohort of recently infected blood donors and a small group of elite controllers in South Africa. Because of the prospective data collection, we will use longitudinal data analysis techniques that account for the clustered nature of the data. That is, there will be multiple time points for each blood donor. Possible outcome variables will represent the time course of early HIV viremia, production of antibody, host immune response, and potential suppression of HIV infection. The predictor variables will be HIV subtype, demographic variables, predictor variables identified in objective 1a, and predictor variables identified in the HIV subtype analysis in objective 2a. These analyses for this objective will be primarily descriptive but may include proportional hazards models.

